## 1 Introduction

### 1.1 Background

It is estimated that 15,000 to 20,000 new cases of Myelodysplastic Syndromes (MDS) are diagnosed annually in the USA ([Klepin 2016](#)). The incidence of MDS is more frequent in male patients and increases with age, with a median age at diagnosis of about 70 years. MDS correspond to a heterogeneous group of hematopoietic diseases that are associated with impaired bone marrow function, ineffective hematopoiesis, elevated bone marrow blasts and persistent peripheral blood cytopenias. Cytogenetics abnormalities are frequently present at time of diagnosis. Patients with MDS have a predisposition to developing acute myeloid leukemia (AML) ([Heaney and Golde 1999](#)). Although progression to AML can frequently lead to death in patients with MDS, many deaths are consequences of cytopenias and marrow failure in the absence of leukemic transformation. To account for disease heterogeneity, assess the risk of progression to AML and estimate survival, MDS prognostication systems have been proposed. Prognosis is usually determined using the revised International Prognostic Scoring System (IPSS-R), which considers the percentage of bone marrow blasts, the number of cytopenias, and bone marrow cytogenetics. Patients with untreated MDS are stratified into five IPSS-R prognostic risk categories: very low, low, intermediate, high and very high, with median survival times of 8.8, 5.3, 3.0, 1.6 and 0.8 years, respectively and with 25% AML transformation rate of NR (not reached), 10.8, 3.2, 1.4, 0.73 years respectively ([Greenberg et al 2012](#)). In a large database of MDS patients (n = 7,012) distribution of patients across the 5 IPSS-R risk categories were as follows: Very low (19%), low (38%), intermediate (20%), high (13%) and very high (10%) ([Greenberg et al 2012](#)). Current treatment guidelines for MDS recommend modification of the disease with hematopoietic stem cell transplantation (HSCT, treatment with a curative intent), hypomethylating agents (HMA: azacitidine or decitabine) or intensive chemotherapy ([Fenaux et al 2014](#)). Choice of therapy is mainly driven by the IPSS-R score, the overall general health status and clinical assessment of comorbidities. For patients eligible for intensive therapy, and for whom a donor is available for HSCT or for whom the marrow blast count requires reduction, intensive chemotherapy may be considered ([Steensma 2018](#)). HSCT remains the only curative option for MDS patients; however, many MDS patients are not candidate for HSCT ([Passweg et al 2011](#); and see [Section 4.3.1](#)). In MDS patients without major co-morbidities who are classified as intermediate, high, very high risk by IPSS-R, and who do not qualify for HSCT or intensive chemotherapy, HMAs remain the first-line reference treatment. HMAs (azacitidine or decitabine) are generally administered for a minimum of 6 cycles (repeat cycle after 4 weeks), and continued for as long as the patient benefits. HMAs (azacitidine or decitabine) have a similar safety profile. In clinical practice, bone marrow suppression is the most common adverse reaction in demethylation therapy, and is also the main reason for the dose-reduction or discontinuations of decitabine or azacitidine. Supportive care, including blood transfusions, is frequently required. HMAs have improved outcomes for patients with intermediate/high risk/very high risk MDS; especially for patients who are not candidates for intensive chemotherapy regimens or HSCT. However, despite these improvements, prognosis for patients treated with HMA remains poor. Complete Remission rate (CR) with azacitidine or decitabine in higher-risk (IPSS; intermediate- & high, IPSS-R; intermediate, high & very high) MDS is rare. CR rate has been shown to be 9% for decitabine and 17 % for azacitidine in pivotal trials ([Kantarjian et al 2006](#), [Fenaux et al 2009](#)). Other trials

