### 5.1 Inclusion criteria

Written informed consent must be signed by the patient prior to any screening procedures. Patients eligible for this study must meet **all** of the following criteria:

1. Signed informed consent must be obtained prior to participation in the study.
2. Age  $\geq 18$  years at the date of signing the informed consent form (ICF).
3. Morphologically confirmed diagnosis of a myelodysplastic syndrome (MDS) primary or secondary based on 2016 WHO classification (Arber et al 2016) by investigator assessment with one of the following Prognostic Risk Categories, based on the International Prognostic Scoring System (IPSS-R). Note: MDS diagnosis history will be recorded in the CRF:
  - Very high ( $> 6$  points)
  - High ( $> 4.5 - \leq 6$  points)
  - Intermediate ( $> 3 - \leq 4.5$  points)
4. Not suitable at time of screening for immediate myeloablative/ chemotherapy or hematopoietic stem-cell transplantation based on investigator assessment of age, comorbidities, local guidelines, institutional practice (any or all of these).
5. Eastern Cooperative Oncology Group (ECOG) performance status of 0, 1 or 2.
6. AST and ALT  $\leq 3 \times$  upper limit of normal (ULN).
7. Total bilirubin  $\leq 2 \times$  ULN (except in the setting of isolated Gilbert syndrome).
8. Estimated Glomerular Filtration Rate (eGFR)  $\geq 30$  mL/min/1.73m^2 (estimation based on Modification of Diet in Renal Disease (MDRD) formula, by local laboratory).
9. Patient is able to communicate with the investigator and has the ability to comply with the requirements of the study procedures.

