### 8.3 Efficacy

Efficacy assessments will be performed according to the IWG and WHO criteria for MDS ([Cheson et al 2000](#), [Cheson et al 2006](#), [Arber et al 2016](#), [Platzbecker et al 2018](#)). Response criteria in MDS are described in [Table 8-2](#). Investigators will assess locally at their site and document response/progression at each time point as per the visit schedule. For efficacy analyses, baseline is defined as the last non-missing assessment on or before the date of enrollment.

The hematological improvement per modified IWG-MDS criteria ([Cheson et al 2006](#)) will be assessed in all enrolled participants to report specific hematologic improvement (HI) of cytopenias in the three hematopoietic lineages: erythroid (HI-E), platelet (HI-P), and neutrophil (HI-N).

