**Table 8-2 Modified response classification per IWG criteria in MDS**

([Platzbecker et al 2018](#), [Cheson et al 2006](#), [Cheson et al 2000](#))

Response category	Definition #
Complete remission (CR)	
Bone marrow:  <math>\leq 5\%</math> blasts with normal maturation of all cell lineages.            (Note: Persistence of dysplasia will be noted but does not preclude achievement of complete remission [CR])
 
Peripheral blood
 
 
1. Hgb <math>\geq 10</math> g/dL AND
 
2. Platelets <math>\geq 100*10^9/L</math> AND
 
3. Neutrophils <math>\geq 1.0*10^9/L</math> AND
 
4. Blasts 0%
 
 
Note: the participant must not receive RBC or platelet transfusions, myeloid growth factor within 2 weeks before this disease assessment

marrow Complete remission (mCR)	
Bone marrow:  <math>\leq 5\%</math> blasts and blast count decrease by <math>\geq 50\%</math> compared to baseline
 
Peripheral blood/transfusion:            Marrow CR may be achieved with or without improved blood counts or with or without transfusions

Partial remission (PR)	All CR criteria except Bone marrow: $\geq 50\%$ decrease from baseline in blasts in bone marrow AND blast count in bone marrow $>5\%$
Stable Disease (SD)	Failure to achieve at least PR, but no evidence of progression for $>8$ weeks

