Relapse from CR	Only in participants with a CR: At least 1 of the following criteria is met: [In absence of another explanation not due to MDS, such as acute infection, bleeding, hemolysis, etc. Note that observation of peripheral blasts is not a sufficient criterion for relapse. However in that case, a bone marrow examination should be made to determine whether relapse has occurred.] 

1. Return to baseline bone marrow blast percentage

2. Decrease of <math>\geq 50\%</math> from maximum remission/response*** levels in neutrophils AND neutrophils <math><1.0*10^9/L</math>. Note: neutrophils counts during periods of active infection will not be considered in determining the maximum

3. Decrease of <math>\geq 50\%</math> from maximum remission/response*** levels in platelets AND platelets <math><100*10^9/L</math>

4. Decrease from maximum remission/response*** levels in Hgb concentration by <math>\geq 1.5\text{g/dL}</math> AND Hgb <math><10\text{ g/dL}</math>

5. Becoming transfusion dependent**

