Disease progression	
At least 1 of the following criteria is met:
 
[In absence of another explanation not due to MDS, such as acute infection, bleeding, hemolysis, etc. Note that observation of peripheral blasts is not a sufficient criterion for progression. However in that case, a bone marrow examination should be made to determine whether relapse has occurred.]
 
Bone marrow according to the number of blasts of the participant at baseline:
 
 
1. Less than 5% blasts at baseline: <math>\geq 50\%</math> increase in blasts over baseline to <math>>5\%</math> blasts
 
2. 5%- <math><10\%</math> blasts at baseline: <math>\geq 50\%</math> increase over baseline to <math>>10\%</math> blasts
 
3. 10%- <math><20\%</math> blasts at baseline: <math>\geq 50\%</math> increase over baseline to <math>>20\%</math> blasts. Participants with more than 20% of blasts will be considered to have transformation to acute leukemia per 2016 WHO classification (Arber et al 2016)
 
 
Peripheral blood:
 
 
1. Decrease of <math>\geq 50\%</math> from maximum remission/response*** levels in neutrophils AND neutrophils <math><1.0 \times 10^9/L</math>. Note: neutrophils counts during periods of active infection will not be considered in determining the maximum
 
2. Decrease of <math>\geq 50\%</math> from maximum remission/response*** levels in platelets AND platelets <math><100 \times 10^9/L</math>
 
3. Reduction from maximum remission/response*** levels in Hgb by <math>\geq 2\text{g/dL}</math> AND Hgb <math><10\text{g/dL}</math>
 
 
Becoming transfusion dependent**
 
Occurrence of acute leukemia or extramedullary leukemia per investigator's judgement

----------------------------	---

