2.7.1.6 Duration of Complete Remission

Duration of Complete Remission (DOR) is the time from the date of the first documented CR to the date of first documented relapse from CR or death due to any cause, whichever occurs first.

The start date is the date of first documented CR and the end date is defined as the date of the first documented relapse from CR or death due to any cause. Duration of CR for Subjects without event will be censored at the date of their last adequate response assessment.

DOR will be analyzed using the Kaplan-Meier method. Estimates of the 25th, median and 75th percentile of the DOR and their 95% confidence intervals will be provided, Kaplan-Meier curves will be produced, if applicable.

- DOR applies only to subjects who have CR (responded).

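### The marrow criterion for relapse from CR has no blast floor, so a participant who entered with 5% blasts or fewer can be recorded as relapsed while still meeting every CR criterion

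*Protocol*

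**What the plan says.** In protocol Table 8-2 (section 8.3), CR requires marrow with at most 5% "blasts with normal maturation of all cell lineages", plus limits for hemoglobin, platelets, neutrophils and peripheral blasts. It asks for no fall from baseline.

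Relapse from CR applies only to participants with a CR and needs one of five criteria. Criterion 1 is "Return to baseline bone marrow blast percentage". Criteria 2 to 4 combine a fall in a blood count with an absolute limit: neutrophils below 1.0, platelets below 100 or hemoglobin below 10. Criterion 5 is transfusion dependence. One qualifier covers the whole row: "In absence of another explanation not due to MDS, such as acute infection, bleeding, hemolysis, etc". SAP Table 2-6 carries the same row with no floor added.

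The progression row of the same table has a stratum headed "Less than 5% blasts at baseline", and it requires a rise of at least 50% that ends above 5%.

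For efficacy, "baseline is defined as the last non-missing assessment on or before the date of enrollment" (protocol 8.3). For CR duration, "the end date is defined as the date of the first documented relapse from CR or death due to any cause" (SAP 2.7.1.6). Relapse from CR is also a PFS event (protocol 12.5.1.2, SAP 2.7.1.2).

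**The concern.** Participants with few marrow blasts are expected in this trial. Eligibility is an IPSS-R score above 3 with no blast minimum (protocol 5.1), and protocol 1.1 describes IPSS-R as a system "which considers the percentage of bone marrow blasts, the number of cytopenias, and bone marrow cytogenetics". The progression stratum for under 5% baseline blasts confirms it.

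Such participants reach CR mainly through recovery of the blood counts, because the marrow condition is already met or nearly met at entry. Criterion 1 then measures relapse against a baseline that itself lies inside the CR range. A small rise back to that value can end the remission on paper while marrow and blood still satisfy CR.

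Three secondary results could be affected. PFS could gain a false event. CR duration could end early. Under the best-response rule in SAP 2.7.1.1, a CR followed soon enough by relapse no longer counts as CR; that rule gives the interval as four but omits the unit. Any bias would fall only on participants with low baseline blasts.

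**Working it through.** The documents give no figure on this point to reproduce. The check has two parts: the logic of the rules, and the scale.

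**Rules.** The marrow rules of Table 8-2 were applied with all CR blood criteria held as met and no transfusions:

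- CR: blasts ≤ 5%.
- Relapse criterion 1: blasts ≥ baseline value.
- Progression: blasts ≥ 1.5 × baseline, and above 5% (baseline < 5%), above 10% (baseline 5% to < 10%) or above 20% (baseline 10% to < 20%).

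Whole-number marrow values from 0% to 30% that satisfy both CR and criterion 1:

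- Baseline 1%: 1% to 5%
- Baseline 2%: 2% to 5%
- Baseline 3%: 3% to 5%
- Baseline 4%: 4% and 5%
- Baseline 5%: 5%
- Baselines 6%, 8%, 10% and 15%: none

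CR and the progression marrow rule do not overlap at any of these baselines. If criterion 1 also requires blasts above 5%, its overlap with CR is empty at every baseline, and nothing changes for baselines of 6% or more.

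**Scale.** Inputs: 39 enrolled (protocol 12.7); CR rates of 10.5% and 33.3% in the azacitidine and decitabine arms of the earlier combination study (protocol 4.3.2); share of CR participants with baseline blasts ≤ 5% not given, assumed 10% to 50%.

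- Expected CRs: 39 × 0.105 = 4.1, and 39 × 0.333 = 13.0.
- Exposed CRs: 4.1 × 0.10 = 0.4, and 13.0 × 0.50 = 6.5.
- One false event as a share of the CR-duration sample: 1/13 = 8%, to 1/4 = 25%.

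**How easily a return could be read.** This is an illustration only. Assume a 500-cell count and independent reads, with a baseline of 3% and true blasts steady at 2% in remission. One count reads between 3% and 5% with probability 0.081. Over three later marrows the chance of at least one such reading is 1 − 0.919³ = 0.22; over two it is 1 − 0.919² = 0.155. With true blasts steady at 1%, the chance over three marrows is about 0.001. The cell count is not in the documents, and a reading becomes an event only if the investigator records it as relapse.

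**The case against.** Relapse is the investigator's judgement, not a programmed derivation. An investigator looking at a participant who meets every CR criterion may well not record a relapse. This stands as a reason to expect few cases, but neither document writes a floor, and the SAP has no check for such calls.

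The wording may follow the cited IWG criteria. The table's footnote says that italics mark modifications, and criterion 1 shows none in the text as extracted. If that formatting is reliable, adding a floor would depart from the standard named in the endpoint, at some cost to comparability. The cited publications are not available here, so this cannot be settled. The table is nonetheless titled as modified, and its own progression row has the floor.

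The endpoints are secondary and descriptive, and the current SAP addendum is dated after database lock (SAP document history). Rewording the tables cannot change calls already made. That limits the remedy to analysis.

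Three stronger readings are tempting, and the documents do not support them:

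- A reader might infer that CR and relapse can be met on one and the same marrow sample. The row speaks of a return, which presupposes an earlier fall; a marrow that never left its baseline value has nothing to return from.
- A reader might infer that false relapses are near certain over successive marrows. That needs an early CR, true blasts that stay at baseline, independent readings and an investigator who records each one.
- A reader might infer that follow-up ends at relapse, so that the error could never be seen. That stop appears only in the extension-phase text (protocol 8.3 and 9.1.5). The core-phase marrows at cycles 4, 7, 10 and 13 and at end of treatment have no such stop, and protocol 9.1.1 continues efficacy assessments after treatment discontinuation.

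**Conclusion.** The gap in the definition is certain on the text. Criterion 1 lacks the absolute limit found in relapse criteria 2 to 4 and in the progression rule for the same low-blast stratum, and nothing else in either document supplies one. A fall followed by a return to a baseline of 5% or less can be recorded as relapse in a participant who is still in CR.

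The effect on the results is uncertain. About 0.4 to 6.5 CR participants are exposed, given the cited CR rates and an assumed low-blast share of 10% to 50% among the CRs. Exposure is not an event, and zero affected participants is plausible. In a CR-duration sample of about 4 to 13, however, even one false relapse would be 8% to 25% of the sample. That justifies a specific check, but no claim that the reported PFS or CR duration is wrong.

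**What to change.** In the SAP, flag every investigator-recorded relapse from CR that rests only on criterion 1 with marrow blasts of 5% or less. Confirm from the blood counts and transfusion records that no other relapse criterion was met. Report PFS, CR duration and best overall response with and without the flagged events. When a flagged relapse is set aside, use the next qualifying event or the SAP's existing censoring rule. If there are no flagged cases, say so in the report.

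If the tables are revised, add a requirement of more than 5% blasts to criterion 1 in protocol Table 8-2 and SAP Table 2-6, so that it agrees with the progression floor, and mark it as a modification of the IWG wording.

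The cost is one extra derivation. SAP 2.7.1 already lists response assessments and marrow blast percentages by subject, so no new procedure is needed. SAP section 4 drops sensitivity analyses, so this one would have to be entered there as an exception. Revising the tables may also cost a little comparability with results under unmodified IWG criteria. For a relapse recorded in the extension phase, later assessments may be missing, and the alternative derivation may then simply censor there.

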#### **6.1.4.1 Treatment beyond disease progression**

Participants with immunotherapy may get clinical benefit despite initial evidence of disease progression. Participants will be allowed to continue the study treatment, (HMA and/or MBG453 (sabatolimab)) beyond disease progression through the extension phase if all four of the following criteria are met:

1. Absence of acute leukemia per WHO 2016 classification (as defined as  $\geq 20\%$  of blasts in bone marrow and/or peripheral blood) ([Arber et al 2016](#))
2. There is a clinical benefit observed per investigator assessment. The clinical benefit at the time of disease progression should consist of :
  - Improved or stable ECOG performance status and no cell lineage (neutrophils count, platelets count, hemoglobin) have worsened by  $>25\%$  as compared to baseline status
  - And, at least one of the two following criteria:
    - Improvement or stabilization of cytopenia in at least one cell lineage (neutrophils count, platelets count, hemoglobin) as compared to baseline values, or
    - Reduction of RBC/platelet transfusion needs within the 8 weeks prior to evidence of disease progression as compared to transfusion needs reported prior to enrollment
3. No unacceptable toxicity is reported
4. The participant continues to follow all protocol requirements

In addition, treatment beyond disease progression should not jeopardize critical interventions to treat/prevent severe complications or prevent participants from receiving adequate care.

If the study treatment continues, the participants should continue to perform all assessments for extension phase as per [Table 8-1](#).

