## **9 Study discontinuation and completion**

### **9.1 Discontinuation and completion**

#### **9.1.1 Discontinuation of study treatment**

Study treatment is considered discontinued if stopped earlier than the protocol planned duration. Either the participant or the investigator can initiate study treatment discontinuation.

The investigator must discontinue study treatment for a given participant if, he/she believes that continuation would negatively impact the participant's well-being.

Study treatment must be discontinued under the following circumstances:

- Participant/guardian decision
- Pregnancy

- Use of prohibited treatment as per recommendations in the prohibited treatment (see [Section 6.2.2](#))
- Any situation in which study participation might result in a safety risk to the participant
- Any adverse events or laboratory abnormalities that in the judgement of the investigator, taking into consideration the participant's overall status, prevents the participant from continuing participation in the study
- Protocol-defined reasons for discontinuation (see [Section 6.1.4](#))
- Progression of disease (including transformation to acute leukemia per WHO 2016 classification, as defined as  $\geq 20\%$  blasts in bone marrow and/or peripheral blood), unless specific criteria to continue study treatment, in case there is no acute leukemia reported, as per [Section 6.1.4.1](#), are met
- Termination of the study by Novartis
- Participants who are scheduled for hematopoietic stem-cell transplant (HSCT) or chemotherapy at any time during the course of the study
- Transition to commercial supplies

If discontinuation of study treatment occurs, the investigator should make a reasonable effort to understand the primary reason for the participant's premature discontinuation of study treatment and record this information.

Participants who discontinue study treatment or who decide they do not wish to participate in the study further should NOT be considered withdrawn from the study UNLESS they withdraw their consent (see [Section 9.1.2](#)). **Where possible, they should return for the assessments indicated** in the Assessment Schedule. If they fail to return for these assessments for unknown reasons, every effort (e.g. telephone, e-mail, letter) should be made to contact the participant/pre-designated contact as specified in the lost to follow-up section ([Section 9.1.3](#)). This contact should preferably be done according to the study visit schedule.

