| Disease progression | 
At least 1 of the following criteria is met:
 
[In absence of another explanation not due to MDS, such as acute infection, bleeding, hemolysis, etc. Note that observation of peripheral blasts is not a sufficient criterion for progression. However in that case, a bone marrow examination should be made to determine whether relapse has occurred.]
 
Bone marrow according to the number of blasts of the subject at baseline:
 
 1. Less than 5% blasts at baseline: $\geq 50\%$ increase in blasts over baseline to $>5\%$ blasts 2. 5%- $<10\%$ blasts at baseline: $\geq 50\%$ increase over baseline to $>10\%$ blasts 3. 10%- $<20\%$ blasts at baseline: $\geq 50\%$ increase over baseline to $>20\%$ blasts. Subjects with more than 20% of blasts will be considered to have transformation to acute leukemia per 2016 WHO classification (Arber et al 2016) 
Peripheral blood:
 
 1. Decrease of $\geq 50\%$ from maximum remission/response*** levels in neutrophils AND neutrophils $<1.0 \times 10^9/L$. Note: neutrophils counts during periods of active infection will not be considered in determining the maximum 2. Decrease of $\geq 50\%$ from maximum remission/response*** levels in platelets AND platelets $<100 \times 10^9/L$ 3. Reduction from maximum remission/response*** levels in Hgb by $\geq 2\text{g/dL}$ AND Hgb $<10\text{g/dL}$ 
Becoming transfusion dependent** Occurrence of acute leukemia or extramedullary leukemia per investigator's judgement
 |
|----------------------------|---|

| Modified Hematological Improvement per IWG-MDS criteria in MDS (Cheson et al 2006) | |
|---|---|
| HI category | Definition[#] (HI must last at least 8 weeks) |
| Erythroid response (HI-E) (pretreatment*, $<11\text{ g/dL}$) | 
 1. Hgb increase from baseline by $\geq 1.5\text{ g/dL}$, in at least 2 consecutive Hgb measurements and maintained over at least 8 weeks 2. Relevant reduction from baseline of units of RBC transfusions by an absolute number of at least 4 RBC transfusions/8 weeks compared with the pre-treatment transfusion number in the previous 8 weeks. Only RBC transfusions given for a Hgb of $<9\text{ g/dL}$ pre-treatment will count in the RBC transfusion response evaluation. |

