2.7.1.4 Leukemia-free survival

Leukemia-free survival (LFS) is the time from the date of enrollment (cycle 1 day 1) to $\geq 20\%$ blasts in bone marrow/peripheral blood (per WHO 2016 classification) or death due to any cause.

For a subject without event, the subject is censored at the latest date the subject was known to be alive and without leukemia (last adequate assessment, bone marrow and/or hematology assessment on or before the cut-off date).

LFS will be analyzed using the Kaplan-Meier Product-Limit method. Estimates of the 25th, median and 75th percentile of the PFS and their 95% confidence intervals will be provided, Kaplan-Meier curves will be produced, if applicable.

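### Table 8-2 and SAP Table 2-6 define leukemic transformation differently from LFS and the discontinuation rule, so an LFS event need not meet the blast criteria used to record PFS

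*Protocol*

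**What the plan says.** Protocol Table 8-2 defines disease progression as meeting at least one listed criterion. After the third marrow criterion (baseline blasts of 10% to <20%) it says: "Participants with more than 20% of blasts will be considered to have transformation to acute leukemia per 2016 WHO classification". The preamble to the same row says: "Note that observation of peripheral blasts is not a sufficient criterion for progression", and asks for a marrow examination in that case. A separate line, with no number and no compartment, also counts as progression: "Occurrence of acute leukemia or extramedullary leukemia per investigator's judgement". SAP Table 2-6 carries the same content: "Subjects with more than 20% of blasts will be considered to have transformation to acute leukemia per 2016 WHO classification".

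Elsewhere the threshold is ≥20% and blood counts as well as marrow:

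- Protocol 9.1.1 lists this among the circumstances that require stopping: "Progression of disease (including transformation to acute leukemia per WHO 2016 classification, as defined as" ≥20% blasts in marrow and/or blood.
- Protocol 6.1.4.1 makes this a condition for continuing beyond progression: "Absence of acute leukemia per WHO 2016 classification", with the same ≥20% definition in marrow and/or blood.
- LFS (Protocol 12.5.1.4, SAP 2.7.1.4) counts as an event ≥20% "blasts in bone marrow/peripheral blood (per WHO 2016 classification) or death due to any cause".

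PFS (Protocol 12.5.1.2, SAP 2.7.1.2) includes transformation per WHO 2016, as assessed by the investigator, and gives no number.

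**The concern.** PFS counts progression including transformation, relapse from CR, and death. LFS counts transformation and death. Every transformation that ends LFS should therefore also end PFS, on or before the same date, unless one of the PFS censoring rules applies. With two definitions of transformation attributed to the same classification, that ordering is not guaranteed.

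The source of the data makes this more than a wording matter. SAP 2.7.1.1 says investigators record response categories in the eCRF as the table defines them, and PFS follows investigator assessment. SAP 2.7.1.4 refers to marrow and/or hematology assessments for LFS. No SAP rule connects the two. At stake is the coherence of two secondary endpoints reported on the same 39 participants: the same blast count could be a failure for LFS and, for PFS, a later event or none.

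**Working it through.** The plan gives no figure to reproduce here, so the check compares definitions. I read the slash in the LFS definition as either compartment, in line with 6.1.4.1 and 9.1.1.

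| Place | Threshold | Blood blasts alone sufficient? |
|---|---|---|
| Protocol Table 8-2, SAP Table 2-6 | >20%, under the marrow criteria | No |
| Protocol 9.1.1 | ≥20% | Yes |
| Protocol 6.1.4.1 | ≥20% | Yes |
| LFS, Protocol 12.5.1.4 and SAP 2.7.1.4 | ≥20% | Yes |
| PFS, Protocol 12.5.1.2 and SAP 2.7.1.2 | none stated | not stated |

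**Marrow route.** Take an on-study marrow of exactly 20%, which meets the ≥20% rule.

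- Baseline below 5%: the table needs a rise of at least 50% to above 5%. Since 1.5 × 5 = 7.5 and 20 > 5, it is met.
- Baseline 5% to <10%: it needs a rise of at least 50% to above 10%. Since 1.5 × 10 = 15 and 20 > 10, it is met.
- Baseline 10% to <20%: it needs a rise of at least 50% to above 20%. At baseline 12%, 1.5 × 12 = 18, so the rise is met, but 20 is not above 20. The sentence on more than 20% also fails.

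Running integer baselines of 1% to 19% against on-study marrows of 20% to 40% gives the same result. There is no gap below a 10% baseline, and the only gap at 10% to 19% is a reading of exactly 20%. This takes the sentence on more than 20% as a criterion in its own right. If it were read only as a comment on the third criterion, the 50% rise would widen the gap. At baseline 15%, 1.5 × 15 = 22.5, so 20% to 22% would be missed. At 19%, 1.5 × 19 = 28.5, so 20% to 28% would be missed. I rely on the narrower reading.

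**Blood route.** At any baseline, ≥20% blasts in blood is an LFS event. If no marrow is done, or the marrow does not meet the marrow criteria, none of the table's blast criteria is met. This gap is wider than the marrow one.

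**Timing.** Protocol 8.3 schedules hematology on Days 1 and 8 of each cycle, and Table 8-5 includes blasts in that panel. Marrow is scheduled at C4D1, C7D1, C10D1, C13D1 and end of treatment, so planned on-treatment marrows are 3 × 28 = 84 days apart. Blood can therefore cross 20% between marrows. Section 8.3 asks for prompt evaluation on suspicion, so a wait of that length is not expected. Even with a prompt marrow, LFS can date from the blood count and PFS from the later marrow.

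**Result in the PFS analysis.** In both cases the investigator-judgement line decides whether a PFS event is recorded, and on which date. The count-based and transfusion-dependence criteria in the table may also be met, but nothing ensures it.

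**The case against.** Much can be said for the plan. Progression needs only one criterion, and acute leukemia in the investigator's judgement is one of them. PFS names WHO 2016 transformation directly, and 6.1.4.1 and 9.1.1 show what the protocol takes that to mean. The marrow case needs one particular reading. The blood case needs the marrow to be missing or not qualifying, although the table asks for one, suspected progression calls for prompt evaluation, and an end-of-treatment marrow is planned. Both endpoints are secondary and descriptive. The current SAP addendum is dated after database lock, so rewording the table cannot alter what investigators recorded. A derived PFS date would also partly override an investigator-assessed endpoint.

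Most of this stands, and it limits the point. It does not remove it, because the judgement line lets a site capture the case but does not require it, while LFS follows a fixed number.

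A reader might infer four stronger things that the documents do not support:

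- **That these participants are lost as PFS events and PFS is biased upward.** The judgement line and the PFS definition can capture both cases. What is shown is dependence on the site's reading.
- **That a site could keep treating a participant who must stop.** Table 8-2 classifies response. Treatment is governed by 9.1.1 and 6.1.4.1, which agree with each other.
- **That these participants would be routed to the extension phase as if not progressed.** 9.1.1 itself classes this as progression.
- **That the effect has a size in percentage points.** One participant is 1/39 = 2.6% of those enrolled, but no document says how many are affected, and a Kaplan-Meier step depends on the number still at risk.

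**Conclusion.** The inconsistency is in the text of both documents and is worth correcting. Two definitions of transformation carry the same citation. Under them, a participant can be an LFS event without meeting the table's blast criteria, and PFS status and date then rest on investigator judgement. The marrow gap is confined to a reading of exactly 20% with baseline blasts of 10% to <20%; the blood gap applies at any baseline. The number affected cannot be computed, because no blast distribution is given. The conclusion assumes that LFS is derived from recorded blast counts and PFS from the investigator's recorded category, which is how SAP 2.7.1 reads. It concerns agreement between two descriptive secondary endpoints and does not touch the primary safety objective. Which clinical threshold or compartment is right is not judged here.

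**What to change.** Reconcile Protocol Table 8-2 and SAP Table 2-6 with Protocol 6.1.4.1, 9.1.1 and 12.5.1.4 and SAP 2.7.1.4, so that one definition, chosen by the sponsor, serves PFS, LFS and discontinuation. State how the peripheral-blast note applies to a count that meets that definition.

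In SAP 2.7.1.2, state that any transformation counted as an LFS event is also a PFS event no later than that date. Say how this sits with the existing PFS censoring for new anti-neoplastic therapy and for events after two or more missed assessments; SAP 2.7.1.4 lists no such rules for LFS.

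Add a programmed check that PFS time ≤ LFS time, and compare event flags as well. A PFS time censored before the LFS date would pass the time check while the event is still missing.

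The cost is one table row in each document, a sentence or two in the SAP and a short program; no new data are needed. PFS may become slightly shorter. In a few cases the derived date may replace the investigator-recorded one, and those cases should be footnoted. Because the database is locked, the practical gain now lies in the SAP derivation and the study report.
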